### **13.3 Statistical Analyses**

Additional details of the proposed statistical analysis will be documented in the statistical analysis plan (SAP), which will be written following finalization of the protocol and prior

Property of Haleon - Confidential

May not be used, divulged, published or otherwise disclosed without the consent of  
Haleon

Clinical Protocol Template, TMF-187821, v11.0. Parent SOP: **CCI** [REDACTED]

to study analysis. This section is a summary of the planned statistical analyses of the most important endpoints including primary and key secondary endpoints.

All data extracted from Actigraph and subjective assessments may undergo visualisation, and graphs will be plotted wherever feasible. For instance, data pertaining to both the daily average number of steps taken and the daily average number of stairs climbed/descended will be presented in sets of charts, graphs, and heatmaps. This approach aims to enable a more thorough analysis, fostering a comprehensive understanding of intricate patterns, trends, and relationships embedded in the dataset. Further information will be provided in the statistical analysis plan (SAP).

### 13.3.1 Primary Analysis

Total study duration is 28 days, with primary analysis performed post baseline (baseline is from Day -7 to Day 0). For primary analysis, average minutes of MVPA on Day 7 will be calculated over all non-missing days between study day 1 (product usage) through 7, inclusive.

Average minutes of MVPA on Day 14 will be calculated over all non-missing days between study day 8 through 14, inclusive. Average minutes of MVPA on Day 21 will be calculated over all non-missing days between study day 15 through 21, inclusive. Any days beyond day 21 will be excluded from all summaries and analyses and will only be present in listed data.

A Mixed Model with Repeated Measures (MMRM) will be used to analyse the change from baseline in MVPA average minutes as the response variable. Subjects will be included as a random effect, and timepoint will be treated as a repeated measure within each subject. If data are found to be non-normal, an appropriate non-parametric test will be performed. If the parameter for the intercept (with compound symmetry structure between visits) is found to be statistically significant ( $p\text{-value} < 0.05$ ), then the individual timepoints (with unstructured covariance structure between visits) will be added as a fixed effect and adjusted means for each timepoint will be presented. P-values and 95% confidence intervals (CIs) for the mean change from baseline in MVPA will be obtained and presented for each timepoint. Other than the global test for an overall change from baseline (i.e., intercept), there will be no other adjustment for multiplicity.

### 13.3.2 Secondary Analysis

For the secondary objective, functional mobility as measured through wearables and PRO, pain intensity assessed through NRS (daily assessment), activity-related pain and stiffness as measured in the WOMAC subscales for composite pain and composite stiffness will be analysed using the same MMRM as in the primary objective where the last observed daily value up to Day 0 will be used as the baseline value.

Correlations of quality of life will also be provided as it pertains to the following:

- Sleep/alertness: Karolinska Sleepiness Scale assessed 1x/day.

Property of Haleon - Confidential

May not be used, divulged, published or otherwise disclosed without the consent of  
 Haleon

Clinical Protocol Template, TMF-187821, v11.0. Parent SOP: **CCI**

- Health-related quality of life: EQ-5D-5L.
- Change in the number of study subjects reporting that they feel more in control of their arthritis pain before and after Voltaren use.

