Safety	
Number and percent of study subjects reporting AEs or serious AEs (SAEs) while on treatment.
 
 
• Treatment Related.
 
• Non-Treatment Related.
 

Statistical Methods and Planned Analyses	
For the primary objective, a Mixed Model with Repeated Measures (MMRM) will be used to analyse the change from baseline in MVPA average minutes as the response variable. Subject will be included as a random effect. Average minutes of MVPA over Week 1 will be calculated over all non-missing days between study day 1 (product usage) through 7, inclusive. Average minutes of MVPA over Week 2 will be calculated over all non-missing days between study day 8 through 14, inclusive. Average minutes of MVPA over Week 3 will be calculated over all non-missing days between study day 15 through 21, inclusive. Any days beyond day 23 will be excluded from all summaries and analyses and will only be present in listed data.
 
For the secondary objective, functional mobility as measured through wearables and PRO, pain intensity assessed through NRS (daily assessment), activity-related pain and stiffness as measured in the (Likert Scale) WOMAC subscales for composite pain and composite stiffness will be analysed in the same manner as the primary objective.
 
For the exploratory endpoints, correlations between pain relief, mobility, and quality of life indices will be measured throughout the trial. Additionally, the use of concomitant medications and any changes in use of pain relief medications will be recorded throughout the trial.
 
Time to pain relief will be evaluated using Kaplan-Meier curves of QoL factors. The median time to resolution of symptoms based on the Kaplan-Meier curve will be presented as well.

---	---

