### **3.5 Changes in the Conduct of Study or Planned Analysis compared to protocol**

Protocol Version Final 4.0 dated 08JUL2024 states in Section 13.2 on page 55 that:

“The modified Intent-To-Treat (mITT) population will include all subjects who use study product at least once and have data from at least one post baseline QoL questionnaire to support at least one of the secondary endpoint assessments. QoL and ePRO data will be summarized using the mITT population only”.

This has been updated in the SAP to include that subjects must meet the inclusion/exclusion criteria to be included in the mITT as below:

“The modified Intent-To-Treat (mITT) population will include all subjects who meet the inclusion/exclusion criteria, who use study product at least once and have data from at least one post baseline QoL questionnaire to support at least one of the secondary endpoint assessments (i.e. have a non-missing response in the ‘Western Ontario and McMaster University Osteoarthritis Index’ or ‘EQ-5D-5L Quality of Life Questionnaire’ eDiary pages). The mITT population will be used for all efficacy analysis.”

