### Baseline

The baseline value for QOL data is defined as measurements collected on Day 0.

Baseline for data collected through connected activity tracker is derived as an average per day:

- Sum of the variable of interest/baseline period.

Where the baseline period is the number of non-missing days between day -6 to day 0 – Prior to product usage.

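### For the secondary tracker endpoints the SAP replaces the protocol's last-daily-value baseline with a multi-day average without declaring it; for NRS it drops the protocol's fallback when Day 0 is missing

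*Protocol*

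**What the plan says.** The baseline rule in protocol 13.3.2 belongs to a sentence that begins "For the secondary objective, functional mobility as measured through wearables and PRO, pain intensity assessed through NRS (daily assessment), activity-related pain and stiffness" and goes on to the WOMAC composite pain and stiffness subscales. For these endpoints it prescribes the primary MMRM and adds that "the last observed daily value up to Day 0 will be used as the baseline value". KSS and EQ-5D-5L come afterwards, under a separate lead-in, "Correlations of quality of life will also be provided as it pertains to the following", with no baseline rule.

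SAP 7.1 has two rules. For the wearable, "Baseline for data collected through connected activity tracker is derived as an average per day", taken over the non-missing days from Day -6 to Day 0. For questionnaires, "The baseline value for QOL data is defined as measurements collected on Day 0". SAP 7.4.7.2 applies the first rule to steps, sedentary ratio, cadence, gait speed and post-wake activity, and the second to NRS, WOMAC and KSS. SAP 8.2.5.1 rules out replacing missing data when endpoints are derived.

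SAP 3.5 lists one departure from the protocol, the mITT definition: "This has been updated in the SAP to include that subjects must meet the inclusion/exclusion criteria to be included in the mITT as below". The SAP document history mentions a revised baseline derivation, but only as a change between SAP versions.

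**The concern.** A single day's reading and a mean of up to seven days are different reference values, so a tracker change score computed under one document is not the one computed under the other. Anyone checking the report against protocol 13.3.2 would find every secondary tracker change measured against an undeclared baseline.

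For NRS the issue is who is analysed. NRS is recorded at Visit 1 and again in the baseline period, so an earlier reading can exist when the Day 0 entry does not. The protocol's rule would use it; the SAP's rule leaves the subject without a baseline.

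**Working it through.** **1. The two documents side by side**

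| Endpoint | Protocol baseline | SAP baseline | Same? |
|---|---|---|---|
| Steps, sedentary ratio, cadence, gait speed, post-wake activity | Last daily value up to Day 0 (13.3.2) | Per-day average, Day -6 to Day 0 (7.1, 7.4.7.2) | No |
| NRS | Last daily value up to Day 0 (13.3.2) | Day 0 only (7.1, 7.4.7.2) | Yes if Day 0 is present; no if missing |
| WOMAC | Last daily value up to Day 0 (13.3.2) | Day 0 only | In practice yes: normally completed once before treatment, on site at Visit 2 |
| KSS, EQ-5D-5L | None stated | Day 0 only | Nothing to compare |
| Primary MVPA change | Baseline period (13.3.1) | Average over the baseline period | The 13.3.2 clause does not apply |

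**2. Sample size.** The stated 147 completers and 195 enrolled do not depend on the disputed clause. With effect size 0.25, two-sided α 0.05 and 80% power, ((1.960 + 0.842)/0.25)² = 125.6. Dividing by the minimum Wilcoxon relative efficiency of 0.864 gives 145.3. The noncentral-t version gives 148, with power 79.8% at 147. Dropout: 147/0.75 = 196. Both stated figures are within one subject.

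**3. NRS.** If Day 0 is missing, the SAP gives no baseline, so there is no change score and no value for the baseline covariate in SAP 8.2.2. The subject leaves the NRS model. The documents give no rate of missing Day 0 entries. Each percentage point would cost between 147 × 0.01 ≈ 1.5 and 195 × 0.01 ≈ 2 subjects, provided an earlier reading exists.

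**4. Tracker precision (illustration).** The documents give no day-to-day variance, so everything here is assumed. Scale the variance of a single day to 1, with between-subject share ICC and day-to-day share w = 1 − ICC. Let τ² be the variance of true change, independent of a subject's level, and nb the number of baseline days. Take seven follow-up days and independent day errors.

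- Raw change: Var = w(1/nb + 1/7) + τ².
- With baseline as a covariate, as in SAP 8.2.2: residual Var = ICC + τ² + w/7 − ICC²/(ICC + w/nb).

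Worked case, ICC 0.5 and τ² = 0.25 × 0.5 = 0.125:

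- Raw: one day 0.5 × 8/7 + 0.125 = 0.696; seven days 0.5 × 2/7 + 0.125 = 0.268; SE ratio √2.6 = 1.61.
- Adjusted: one day 0.696 − 0.250 = 0.446; seven days 0.696 − 0.4375 = 0.259; SE ratio √1.72 = 1.31.

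| SE ratio, one-day to seven-day baseline | Raw change | Baseline-adjusted |
|---|---|---|
| τ² = 0, ICC 0.5 | 2.00 | 1.55 |
| τ² = 0, ICC 0.8 | 2.00 | 1.83 |
| τ² = 0.25 × ICC, ICC 0.5 | 1.61 | 1.31 |
| τ² = 0.25 × ICC, ICC 0.8 | 1.29 | 1.23 |

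Against a three-day baseline, the SAP's minimum number of valid days, the raw ratio with τ² = 0 is √[(1 + 1/7)/(1/3 + 1/7)] = √2.4 = 1.55. If day errors are autocorrelated (AR(1), τ² = 0), the raw variance ratio against seven days falls from 4.0 to 2.9, 2.1 and 1.4 at lag-1 correlations 0.2, 0.4 and 0.6, that is SE ratios of about 1.7, 1.4 and 1.2.

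**The case against.** The best defence is that the protocol is not of one mind. Its synopsis says that these endpoints "will be analysed in the same manner as the primary objective", and section 13.3.1 states for the primary analysis that "baseline is from Day -7 to Day 0". Section 9.2.1 sets the baseline period at three to seven days so that enough mobility data are gathered. Section 13.3 describes itself as a summary, with details left to the SAP. An averaged tracker baseline fits all of that. This stands as a reason to prefer the SAP's rule. It does not remove the specific clause in 13.3.2, which the SAP replaces rather than elaborates, and it shows that the protocol itself needs reconciling.

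It is also fair that the precision loss belongs to the rule the SAP did not adopt, so declaring the change alters no tracker result.

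A reader might infer three stronger things that the documents do not support:

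- That the clause governs every secondary endpoint. It does not reach KSS or EQ-5D-5L, and daily MVPA is not defined as a change score.
- That the SAP removes a protocol fallback for KSS. Section 13.3.2 gives KSS none. Daily KSS readings before Day 0 are not clearly scheduled either: footnote b of the schedule places KSS on site on Day 0 and at home afterwards.
- That questionnaire changes differ in general. They are completed on site on Day 0 before dispensing, so the last value up to Day 0 is the Day 0 value whenever it exists.

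**Conclusion.** The point holds in two limited parts and is minor. First, the secondary tracker endpoints have different baselines in the two documents, and SAP 3.5 is silent. This is a documentation gap; the SAP's rule is explicit and the better of the two. Second, the SAP's NRS rule drops any subject with a missing Day 0 entry whom the protocol's rule would keep. That can change the NRS analysis set, by an amount the documents do not allow one to estimate.

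The direction of the tracker comparison is safe under the settings examined: averaging was more precise in all of them. Its size is not established. The range of about 1.2 to 2.0 in standard error rests on assumed variances, the factor of 2.0 requires independent days and no variation in true change, and the gain is smaller once baseline is a covariate. It should not be turned into an equivalent number of subjects.

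**What to change.** 1. Keep the averaged tracker baseline. Either correct protocol 13.3.2, or add an entry to SAP 3.5 saying that steps, sedentary ratio, cadence, gait speed and 30/60-minute post-wake activity use the SAP 7.1 average in place of the last daily value.
2. In SAP 7.1, restore the protocol's rule for NRS: if the Day 0 value is missing, use the last value observed before Day 0 and before first gel use.
3. Report how many subjects had a missing Day 0 NRS and how many used an earlier value.

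The cost is a few lines of text and one derivation for NRS, all from data already collected. No change is needed for WOMAC, KSS, EQ-5D-5L, primary MVPA or the sample size.

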### **13.3.3 Safety Analysis(es)**

All AEs will be coded using MedDRA. AEs will be categorized as related, probable, unlikely, or unrelated by responsible authority prior to database lock. The number of AEs/SAEs and number of subjects with AEs/SAEs will be listed and tabulated.

### **13.3.4 Exploratory Analysis(es)**

For the exploratory endpoints, correlations between pain relief, mobility, and quality of life indices will be measured throughout the trial. Additionally, the use of concomitant medications and any changes in use of pain relief medications will be recorded throughout the trial.

Time-to-pain relief will also be measured after use of the test product; this will be measured as the elapsed time from test product use to achieving sufficient pain relief to stop using the product and will be evaluated using Kaplan-Meier curves.

### **13.3.5 Exclusion of Data from Analysis**

Any reasons for exclusion from an analysis population will be listed, if applicable.

### **13.3.6 Demographic and Baseline Characteristics**

Age and other continuous demographic and baseline variables will be summarized using descriptive statistics such as mean, range, median and standard deviation. Gender and other categorical demographic and baseline variables will be summarized using frequency counts and percentages for the safety and mITT populations.

## **12.3.6 Study Drug/Product Compliance and Use of Other Therapies**

### **13.3.6.1 Study Drug/Product Compliance**

Compliance and product use will be monitored throughout the study via eDiary and data transfers from Actigraph by relevant study personnel (Site Staff, CRO and Sponsor study team).

Study product compliance will be tabulated and summarized for the safety population. Summaries will include a simple yes/no frequency (and percent) count at each timepoint.

### **13.3.6.2 Prior and Concomitant Medications**

Concomitant medications taken during the study will be listed for the safety population.

### **13.3.7 Handling of Dropouts and Missing Data**

Missing data due to general dropout/withdrawals will be assessed on an ongoing basis during the study. Any further sensitivity analyses needed due to missing data will be reviewed at the time of data review. Additional details will be provided in the data management plan and reporting and statistical analysis plan.

### **13.3.8 Interim Analysis**

No interim analysis is planned for this study.

## **14 STUDY GOVERNANCE CONSIDERATIONS**

### **14.1 Quality Control**

In accordance with applicable regulations including GCP, and Haleon procedures, Haleon or designee (i.e., **CCI**) monitors will contact the site prior to the start of the study to review with the site staff the protocol, study requirements, and their responsibilities to satisfy regulatory, ethical, and Haleon requirements.

When reviewing data collection procedures, the discussion will include identification, agreement, and documentation of data items for which the eCRF will serve as the source document.

Haleon or designee will monitor the study and site activity to verify that the:

- Data are authentic, accurate, and complete.
- Safety and rights of subjects are being protected.
- Study is conducted in accordance with the currently approved protocol and any other study agreements, GCP, and all applicable regulatory requirements.

The extent and nature of monitoring will be described in a written monitoring plan on file at Haleon. The investigator (or designee) agrees to allow the monitor direct access to all relevant documents and agrees to co-operate with the monitor to ensure that any problems detected during these monitoring visits are resolved.

### **14.2 Quality Assurance**

To ensure compliance with GCP and all applicable regulatory requirements, Haleon may conduct a quality assurance assessment and/or audit of the site records, and the regulatory agencies may conduct a regulatory inspection at any time during or after completion of the study.

In the event of an assessment, audit or inspection, the investigator (and institution) must agree to grant the advisor(s), auditor(s) and inspector(s) direct access to all relevant documents and to allocate their time and the time of their staff to discuss the conduct of

Property of Haleon - Confidential

May not be used, divulged, published or otherwise disclosed without the consent of  
Haleon

Clinical Protocol Template, TMF-187821, v11.0. Parent SOP: **CCI**

the study, any findings/relevant issues and to implement any corrective and/or preventative actions to address any findings/issues identified.

The investigator will notify Haleon or its agents immediately of any regulatory inspection notification in relation to the study. Furthermore, the investigator will cooperate with Haleon or its agents to prepare the study site for the inspection and will allow Haleon or its agent, whenever feasible, to be present during the inspection. The investigator will promptly apply copies of the inspection finding to Haleon or its agent. Before response submission to the regulatory authority, the investigator will provide Haleon or its agents with an opportunity to review and comment on responses to any such findings.

The sponsor will be available to help investigators prepare for an inspection.

### **14.3 Regulatory and Ethical Considerations**

#### **14.3.1 Institutional Review Board/ Ethics Committee**

It is the responsibility of the investigator to have prospective approval of the study protocol, protocol amendments, informed consent and/or assent documents, investigator brochure/safety statement (including any updates) and other relevant documents, e.g. recruitment advertisements, if applicable, from the IRB/EC. All correspondence with the IRB/EC should be retained in the investigator file. Copies of IRB/EC approvals should be forwarded to Haleon prior to the initiation of the study, and also when subsequent amendments to the protocol are made.

The only circumstance in which an amendment may be initiated prior to IRB/EC approval is where the change is necessary to eliminate apparent immediate hazards to the subjects. In that event, the investigator must notify the IRB/EC and Haleon in writing immediately after the implementation.

#### **14.3.2 Ethical Conduct of the Study**

The study will be conducted in accordance with the protocol and legal and regulatory requirements. The study will be conducted in compliance with the EU Clinical Trial Regulation 536/2014, as well as the general principles set forth in the International Ethical Guidelines for Biomedical Research Involving Human Subjects (Council for International Organizations of Medical Sciences 2002), International Ethical Guidelines for Health-Related Research Involving Humans (Council for International Organizations of Medical Sciences, 2016), guidelines for GCP (ICH 1996 and revision 2), and the Declaration of Helsinki (World Medical Association 2013).

#### **14.3.3 Subject Information**

All parties will ensure protection of subject personal data and will not include subject names or other identifiable data in any reports, publications, or other disclosures, except where required by laws.

Property of Haleon - Confidential

May not be used, divulged, published or otherwise disclosed without the consent of  
Haleon

Clinical Protocol Template, TMF-187821, v11.0. Parent SOP: **CCI**

When study data are compiled for transfer to Haleon and other authorized parties, subject names, addresses, and other identifiable data will be replaced by numerical codes based on a numbering system provided by Haleon in order to de-identify study subjects.

The study site will maintain a confidential list of subjects who participated in the study, linking each subject's numerical code to his or her actual identity. In case of data transfer, Haleon will maintain high standards of confidentiality and protection of subjects' personal data consistent with applicable privacy laws.

#### **14.3.4 Subject Recruitment**

Advertisements approved by IRBs/ECs and investigator databases may be used as recruitment procedures. Use of ethics committee approved generic, pre-screening questionnaire to assess basic subject characteristics to determine general eligibility for this study is allowed. This generic questionnaire may be used by sites as a phone script and/or to review internal databases to identify subjects.

Haleon will have an opportunity to review and approve the content of any study recruitment materials directed to potential study subjects before such materials are used.

#### **14.3.5 Reporting of Safety Issues and Serious Breaches of the Protocol or ICH GCP**

Within Haleon a serious breach is defined as a breach likely to affect to a significant degree the safety and rights of a subject or the reliability and robustness of the data generated in Haleon -sponsored human subject research studies.

In the event of any prohibition or restriction imposed (i.e., clinical hold) by an applicable competent authority in any area of the world, or if the investigator is aware of any new information that might influence the evaluation of the benefits and risks of the investigational product, Haleon should be informed immediately.

In addition, the investigator will inform Haleon immediately of any urgent safety measures taken by the investigator to protect the study subjects against any immediate hazard, and of any serious breaches of this protocol, of ICH GCP or of the EU Clinical Trial Regulation 536/2014 that the investigator becomes aware of.

In compliance with Article 52 of the EU Clinical Trial Regulation 536/2014, Haleon will notify the member states concerns at the time of the breach through the EU portal without undue delay but not later than seven days of becoming aware of that breach.

